Clinical Trial Protocol

Document Number:		c19558808-06
EudraCT No.: EU Trial No.:	Not applicable.	
BI Trial No.:	1199-0324	
BI Investigational Product(s):	Nintedanib	
Title:	Study of Pulmonary Rehabilitation In Nintedanib Treated Patients with IPF: Improvements in Activity, Exercise Endurance Time, and QoL	
Lay Title:	Study of pulmonary rehabilitation in patients with Idiopathic Pulmonary Fibrosis (IPF)	
Clinical Phase:	IV	
Clinical Trial Leader:	[REDACTED]	
Coordinating Investigator:	[REDACTED]	
Status:	Final Protocol (Revised Protocol based on Global Amendment 2)	
Version and Date:	Version: 3.0	Date: 16 Dec 2019
Page 1 of 103		
Proprietary confidential information. © 2019 Boehringer Ingelheim International GmbH or one or more of its affiliated companies. All rights reserved. This document may not - in full or in part - be passed on, reproduced, published or otherwise used without prior written permission.		

CLINICAL TRIAL PROTOCOL SYNOPSIS

Company name	Boehringer Ingelheim
Finished product name	OFEV
Active ingredient name:	Nintedanib
Protocol date	15 Aug 2018
Revision date	16 Dec 2019
Trial number	1199-0324
Title of trial:	Study of Pulmonary Rehabilitation In Nintedanib Treated Patients with IPF: Improvements in Activity, Exercise Endurance Time, and QoL
Coordinating Investigator:	
Trial site(s):	Multicenter
Clinical phase:	IV
Objective(s):	
Determine the difference in change from baseline in 6MWD when pulmonary rehabilitation (PR) is added to stable underlying nintedanib therapy in patients with idiopathic pulmonary fibrosis (IPF)
 
Determine the difference in change in Quality of Life (QoL) when pulmonary rehabilitation (PR) is added to stable underlying nintedanib therapy in patients with idiopathic pulmonary fibrosis (IPF)
 
Determine if there is an enduring effect in 6MWD, QoL and lung function from pulmonary rehabilitation (PR) when pulmonary rehabilitation (PR) is added to stable underlying nintedanib therapy in patients with idiopathic pulmonary fibrosis (IPF)

Methodology:	Multi-centre, prospective, randomised, open label clinical trial
Number of patients entered:	290 (96 sub-study)
Number of patients on each treatment:	145 (48 sub-study)
Diagnosis:	Idiopathic Pulmonary Fibrosis (IPF) according to American Thoracic Society (ATS), European Respiratory Society (ERS), Japanese Respiratory Society (JRS), and Latin American Thoracic Association (ALAT) criteria published in 2011, consistent with INPULSIS criteria Inclusion
Main in- and exclusion criteria	
 Age \geq 40 years. Forced Vital Capacity (FVC) \geq 45% of predicted

	
 • FEV₁/FVC greater than/equal to .7 and Carbon Monoxide Diffusion Capacity (DL_{CO}) (corrected for hemoglobin [Hgb]) 30-79% of predicted • Confirmed diagnosis of IPF according to 2011 ATS/ERS/JRS/ALAT guidelines by High Resolution Computed Tomography (HRCT) (consistent with INPULSIS criteria) or lung biopsy taken within 24 months prior to providing Informed Consent • Treated on a stable dose of nintedanib for up to 30 months. Patients who have recently started nintedanib 150 mg BID and have started by the day of randomization must be on nintedanib 150 mg BID a minimum of 10 days by the first day of pulmonary rehabilitation. 
Exclusion
 
 • Major surgery within 12 weeks prior to randomization or planned within 6 months after screening which could interfere with the ability to participate in pulmonary rehabilitation • Active or suspected malignancy or history of malignancy within 3 years prior to screening • Currently enrolled in or less than 30 days since ending another interventional investigational device or drug trial • Women who are pregnant, nursing, or who plan to become pregnant in the trial • Previous participation in pulmonary rehabilitation program within 45 days prior to signing informed consent
Test product(s):	nintedanib
dose:	150 mg BID
mode of administration:	oral
Comparator products:	None
dose:	NA
mode of administration:	NA
Duration of treatment:	24 weeks
Endpoints	
 • Primary Endpoint 
 ○ Change from baseline in 6MWD at 12 weeks • Secondary Endpoints 
 ○ Change from baseline in QoL (SGRQ, KBILD, UCSD SOBQ) at 12 and 24 weeks ○ Change from baseline in 6MWD at 24 weeks ○ Change from baseline in lung function (FVC) at 12 weeks and 24 weeks using each of

	
 • Absolute change from baseline of FVC and FVC % predicted • Relative change from baseline of FVC and FVC % predicted • Absolute categorical change of FVC % predicted up to 12 and 24 weeks: decrease by >5%, increase by >5%, and change within ≤ 5 • Absolute categorical change of FVC% predicted up to 12 and 24 weeks: decrease by >10, increase by >10, and change within ≤ 10 
○ Change from baseline in daily accelerometer activity from baseline at 12 and 24 weeks
 
[REDACTED]

Safety criteria:
	
 • Vital signs, physical examination, weight • Clinical laboratory tests (haematology, clinical chemistry, and urinalysis) • Reporting of adverse events • 12 lead electrocardiogram

Statistical methods:
	
The primary (6MWD at 12 weeks) will be analysed using the Analysis of Covariance model including intervention as a fixed categorical covariate and baseline 6MWD as continuous covariate
 
6MWD will be analysed on the original scale. [REDACTED]
 
[REDACTED] all other assessments will be analysed using original scales.

	
For secondary [REDACTED] endpoints, 12-week endpoints will be analysed using similar ANCOVA methodology as the primary endpoint. The 24-week endpoints will be analyzed using a mixed model with repeated measures.
 
Descriptive statistics will be shown for all efficacy and safety endpoints.

--	---

FLOW CHART

	Screening		Interventional Period					
	0	1	Treatment					
Visit	0	1	2	3	4	5	6	7 (EOT)
Weeks of treatment	-2	-1	0	3	6	12	18	24 ⁶
Day	At least 7 days before visit 1	≥ 7d before V 2	1	22	43	85	127	169
Time window				±3	±3	±3	±3	±7
Informed consent	X*							
Demographics/ baseline conditions		X						
Medical history		X						
In-/exclusion criteria	X	X	X					
Physical examination ⁷ , vital signs		X	X	X	X	X	X	X
Laboratory test		X	X	X	X	X	X	X
Pregnancy test		X	X	X	X	X	X	X
Spirometry (FVC)		X	X			X		X
SpO ₂ (peripheral capillary oxygen saturation)		X	X			X		X
DL _{CO}		X	X			X		X
HRCT sent for outcomes review ¹		X ¹	X ¹					
12-lead electrocardiogram (ECG)		X						X
(Practice) Six-minute walk test		X						
Six minute walk test			X			X		X
		■	■			■		■
Instruct Patient on Activity Monitoring and PROactive tool (eDiary) ²	X	X	X		X		X	
Activity Monitoring (Dynaport)	X	X	X			X		X
SGRQ, KBILD, UCSD SOBQ		X	X			X		X
PROactive Tool ^{2,3}	X	X	X			X		X
Randomisation			X					
Schedule pulmonary rehab days for assigned patients ⁶			X					
Record pulmonary rehab				X	X	X		
IRT	X	X ⁵	X					
Adverse events, concomitant treatments		X	X	X	X	X	X	X
Conclude subject participation								X

* Informed consent needs to be signed before any procedure related to the study, all AEs and Concomitant Treatments occurring after the Informed consent have to be recorded.

¹ HRCT will be acceptable if done within 24 months, if not available patient will be sent for HRCT between Visit 1 and 2, or within 7 days of completing Visit 2.

² Patients will wear the physical activity monitor and complete the eDiary (PROactive Tool) 24 hours every day for 1 week prior to Visits 1, 2, 5 and 7. Devices will be dispensed in clinic at Visits 0 and 1, and will be shipped to patient or picked up from clinic at least 1 week prior to Visits 5 and 7.

³

exercise testing center. The incremental and practice tests can both be done at Visit 1.

⁵ Access IRT to terminate if screen fail at Visit 1 or between Visit 0 and Visit 1.

- ⁶ Time between visits 2 and 3 may be extended for up to 6 weeks to allow scheduling of the onset of pulmonary rehabilitation, the treatment period will begin on the first day of pulmonary rehabilitation and all visits move accordingly to keep the same visit schedule.
- ⁷ Height and weight to be collected at Visit 1 only.

TABLE OF CONTENTS

TITLE PAGE	1
CLINICAL TRIAL PROTOCOL SYNOPSIS	2
FLOW CHART	6
TABLE OF CONTENTS	8
ABBREVIATIONS	12
1. INTRODUCTION.....	15
1.1 MEDICAL BACKGROUND.....	15
1.2 DRUG PROFILE	15
1.3 RATIONALE FOR PERFORMING THE TRIAL	15
1.4 BENEFIT - RISK ASSESSMENT.....	16
2. TRIAL OBJECTIVES AND ENDPOINTS.....	17
2.1 MAIN OBJECTIVES, PRIMARY AND SECONDARY ENDPOINTS.....	17
2.1.1 Main objectives.....	17
2.1.2 Primary endpoint(s).....	17
2.1.3 Secondary endpoint(s)	17
3. DESCRIPTION OF DESIGN AND TRIAL POPULATION.....	19
3.1 OVERALL TRIAL DESIGN AND PLAN	19
3.2 DISCUSSION OF TRIAL DESIGN, INCLUDING THE CHOICE OF CONTROL GROUP(S)	19
3.3 SELECTION OF TRIAL POPULATION	19
3.3.1 Main diagnosis for trial entry	20
3.3.2 Inclusion criteria	20
3.3.3 Exclusion criteria	21
3.3.4 Withdrawal of patients from therapy or assessments	21
3.3.4.1 Withdrawal from trial treatment	22
3.3.4.2 Withdrawal of consent for trial participation.....	22
3.3.4.3 Discontinuation of the trial by the sponsor	22
4. TREATMENTS.....	24
4.1 INVESTIGATIONAL TREATMENTS	24
4.1.1 Identity of the investigational medicinal products.....	24
4.1.2 Selection of doses in the trial.....	24

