4. TREATMENTS

4.1 INVESTIGATIONAL TREATMENTS

4.1.1 Identity of the investigational medicinal products

No study medication is included in this trial, this trial is a comparison of pulmonary rehabilitation versus standard care in patients with IPF already taking a stable dose of nintedanib. The active treatment arm will consist of a standard pulmonary rehabilitation regimen two or three times weekly for 12 weeks. Patients assigned to PR will be referred to a facility convenient for the patient. The pulmonary rehabilitation should follow the facility's standard regimen as long as the regimen meets basic standards (to be provided in the ISF). No study specific data collection is required by the PR facility, however standard treatment reports must be available to the investigator to document the attendance and progress of PR.

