5.2.6 Assessment of adverse events

5.2.6.1 Definitions of AEs

Adverse event

An adverse event (AE) is defined as any untoward medical occurrence in a patient or clinical investigation subject administered a medicinal product and which does not necessarily have to have a causal relationship with this treatment.

An AE can therefore be any unfavourable and unintended sign (including an abnormal laboratory finding), symptom, or disease temporally associated with the use of a medicinal product, whether or not considered related to the medicinal product.

Adverse reaction

An adverse reaction (ADR) is defined as a response to a medicinal product which is noxious and unintended. Response in this context means that a causal relationship between a medicinal product and an adverse event is at least a reasonable possibility. Adverse reactions may arise from use of the product within or outside the terms of the marketing authorisation or from occupational exposure. Conditions of use outside the marketing authorization include off-label use, overdose, misuse, abuse and medication errors.

Serious adverse event

A serious adverse event is defined as any AE which

- results in death,
- is life-threatening,
- requires in-patient hospitalization, or
- prolongation of existing hospitalisation,
- results in persistent or significant disability or incapacity, or
- is a congenital anomaly/birth defect

Life-threatening in this context refers to a reaction in which the patient was at risk of death at the time of the reaction; it does not refer to a reaction that hypothetically might have caused death if more severe.

Medical and scientific judgement should be exercised in deciding whether other situations should be considered serious reactions, such as important medical events that might not be immediately life threatening or result in death or hospitalisation but might jeopardise the patient or might require intervention to prevent one of the other outcomes listed above. Examples of such events are intensive treatment in an emergency room or at home for allergic bronchospasm, blood dyscrasias or convulsions that do not result in hospitalisation or development of dependency or abuse. Any suspected transmission via a medicinal product of an infectious agent is also considered a serious adverse reaction.

Adverse events of special interest (AESIs)

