5.2.6.2 Adverse event and serious adverse event collection and reporting

The investigator shall maintain and keep detailed records of all AEs in their patient files.

Collection of AEs

The study design is of non-interventional nature regarding study medication and the study is conducted within the conditions of the approved marketing authorisation. Sufficient data from controlled interventional trials are available to support the evidence on the safety and efficacy of the studied BI drug. For this reason the following AE collection and reporting requirements have been defined.

The following must be collected by the investigator from signing the informed consent onwards until the end of the study:

- all Serious Adverse Events (SAEs) (regardless of causality),
- all Non-serious ADRs
- and AESIs

All SAEs, all non-serious ADRs, and AESIs including those persisting after study completion must be followed up until they are resolved, have been sufficiently characterized, or no further information can be obtained.

The investigator carefully assesses whether an AE constitutes an ADR using the information below.

Causal relationship of adverse event

The definition of an adverse reaction implies at least a reasonable possibility of a causal relationship between a suspected medicinal product and an adverse event. An adverse reaction, in contrast to an adverse event, is characterised by the fact that a causal relationship between a medicinal product and an occurrence is suspected.

Medical judgment should be used to determine the relationship, considering all relevant factors, including pattern of reaction, temporal relationship, de-challenge or re-challenge, confounding factors such as concomitant medication, concomitant diseases and relevant history.

Arguments that may suggest a **reasonable causal relationship** could be:

- The event is **consistent with the known pharmacology** of the drug
- The event is known to be caused by or **attributed to the drug class**.
- A **plausible time to onset of the event** relative to the time of drug exposure.

- Evidence that the **event is reproducible** when the drug is re-introduced
- **No medically sound alternative etiologies** that could explain the event (e.g. preexisting or concomitant diseases, or co-medications).
- The event is typically **drug-related and infrequent in the general population** not exposed to drugs (e.g. Stevens-Johnson syndrome).

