7.3.4 Safety analyses

Analysis of adverse events will be restricted to nintedanib-related serious adverse events, nintedanib-non-related serious adverse events and events of special interest.

Adverse events will be coded using the Medical Dictionary for Drug Regulatory Activities (MedDRA). Standard BI summary tables and listings will be produced. Adverse events with an onset between start of pulmonary rehabilitation treatment and end of trial will be assigned to the on-treatment period for evaluation. All randomized patients will be included in the safety analysis. In general, safety analyses will be descriptive in nature and will be based on BI standards. No hypothesis testing is planned.

Frequency, severity, and causal relationship of adverse events will be tabulated by system organ class and preferred term after coding according to the current version of the Medical Dictionary for Drug Regulatory Activities at the database lock.

Vital signs, physical examinations, or other safety-relevant data observed at screening, baseline, during the course of the trial and at the end-of-trial evaluation will be assessed with regard to possible changes compared to findings before start of pulmonary rehabilitation.

Analysis of laboratory data and electrocardiogram is not planned.

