An overall summary of adverse events will be presented. The frequency of subjects with AEs will be summarised by treatment, primary system organ class and PT (mention MedDRA levels to be displayed in the tables). Separate tables will be provided for subjects with other significant adverse events according to ICH E3 (10), for subjects with significant non-serious adverse events (only if these are defined for the project) and for subjects with serious adverse events (SAEs).

The system organ classes will be sorted by default alphabetically, PTs will be sorted by frequency (within SOC). Customized sorting orders may also be used based on trial needs, e.g. SOC sorted by frequency.

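### The documents do not settle which adverse events enter the CRF, and non-serious harms of pulmonary rehabilitation have no required collection category and no place in the restricted AE analysis

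*Protocol*

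**What the plan says.** **What is tested.** Protocol 4.1.1 states that "this trial is a comparison of pulmonary rehabilitation versus standard care". No study drug is supplied.

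**What is recorded or collected.** The flow chart footnote says that "all AEs and Concomitant Treatments occurring after the Informed consent have to be recorded". Section 5.2.6.2 first asks the investigator to document every AE in the patient's file. It then introduces a closed list with "The following must be collected by the investigator from signing the informed consent onwards until the end of the study". The list is SAEs of any causality, non-serious ADRs and AESIs. Section 8.3.1 names AEs among the data from which the CRF is filled, as an item separate from SAEs.

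**Definitions.** Under 5.2.6.1, "An adverse reaction (ADR) is defined as a response to a medicinal product which is noxious and unintended". The reporting table in 5.2.6.2 narrows non-serious ADRs to those associated with nintedanib. The AESIs are gastrointestinal perforation and hepatic injury.

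**Reason given for the short list.** "The study design is of non-interventional nature regarding study medication", together with the existing safety evidence on the marketed drug (5.2.6.2). Rehabilitation is not mentioned.

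**What is analysed.** Protocol 7.3.4: "Analysis of adverse events will be restricted to nintedanib-related serious adverse events, nintedanib-non-related serious adverse events and events of special interest". SAP 7.8 repeats this. SAP 7.8.1 then says "An overall summary of adverse events will be presented" and plans a separate table of other significant AEs, a category that it defines as non-serious.

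**The concern.** The AE rules are built around a drug that both arms already take and that the trial does not test. The randomised difference between the arms is rehabilitation, and the protocol expects it to cause some harm. Section 4.2.1.2 speaks of AEs related to rehabilitation and to the walk test, and Appendix 10.1.1 lists musculoskeletal injury, fainting and dizziness among the known complications of exercise challenges.

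Two things are at stake. First, the report may be unable to describe the non-serious tolerability of the intervention under study. Second, if sites differ in which non-serious AEs they enter, any table that goes beyond SAEs and AESIs cannot be read without knowing what each site entered.

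**Working it through.** No arithmetic bears on this point, so the check follows one event through the rules. Take a non-serious muscle strain at a rehabilitation session, after which the patient carries on.

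1. **Is it an SAE?** No, unless the investigator judges it an important medical event under 5.2.6.1.
2. **Is it a non-serious ADR?** No. An ADR is a response to a medicinal product, and the reporting table refers to nintedanib.
3. **Is it an AESI?** No. It is neither gastrointestinal perforation nor hepatic injury.
4. **Must it be collected under the 5.2.6.2 list?** By steps 1 to 3, no.
5. **Is it in the patient file?** Yes, by the opening sentence of 5.2.6.2.
6. **Is it in the CRF?** The documents do not settle this:

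| Place | Points to |
|---|---|
| Flow chart footnote | All AEs recorded, location not stated |
| Protocol 5.2.6.2 | All AEs in the patient file; only the three listed groups collected |
| Protocol 8.3.1 | AEs are CRF data, apart from SAEs |
| SAP 7.8.1 | Non-serious AE data expected for the other-significant table |

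7. **Is it analysed if it does reach the CRF?** Not under protocol 7.3.4 or SAP 7.8, which admit only SAEs and AESIs. Following the broad footnote alone would therefore not close the gap.
8. **Could it appear under SAP 7.8.1?** Possibly, in the overall summary if that summary is not bound by the restriction in 7.8. It could also enter the other-significant table, but only if it met a criterion there, such as a recorded action of discontinuation or reduction, or significant concomitant therapy. The relationship attribute in 7.8.1 is drug-relatedness, so the SAP names no field that would mark the event as due to rehabilitation.

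There are side routes into the database for some events of this kind:

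- The reason for withdrawal from trial treatment goes into the CRF and is reported (3.3.4.1).
- The reason for stopping a walk test early is recorded, and the test assessments are transferred to the electronic data capture system (Appendix 10.1.2).
- Information from rehabilitation reports is entered at Visits 3, 4 and 5 (6.2.2). Section 4.1.1 describes these reports as documenting attendance and progress, and asks for no study-specific data from the facility.

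None of these routes reliably captures the strain in the example.

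**The case against.** The strongest reply is that the rules form two tiers: every AE in the source record, and a defined subset passed to the sponsor. The opening sentence of 5.2.6.2 supports this, and the footnote's silence on location permits it. Selective collection is a stated choice for a marketed drug, and section 1.4 calls rehabilitation a standard part of care. The reply has force. A reader might infer that the footnote and 5.2.6.2 flatly contradict each other, and the documents do not support that. What remains is that no passage states the two-tier reading, while 8.3.1 and SAP 7.8.1 suggest wider capture. The two-tier reading also leaves the missing category as it is, and the reason given for the short list covers only the drug.

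A reader might also infer that every non-serious harm of rehabilitation is lost. That goes too far, because events can surface as withdrawal reasons, walk-test stop reasons or events judged serious.

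Nor does the ambiguity make all AE tables a mixture of reporting practices. SAEs and AESIs must be captured under either reading, so the tables confined to them are unaffected. Only the overall summary and the other-significant table are exposed.

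Finally, the current SAP was written after the trial was terminated (SAP section 4), so new prospective collection may no longer be possible. That limits the remedy but leaves the gap in the plan.

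**Conclusion.** The point stands as an unreconciled CRF scope together with a missing category. Non-serious AEs caused by rehabilitation or exercise testing are not in the required collection list and are outside the AE analysis in protocol 7.3.4 and SAP 7.8. The other-significant table in SAP 7.8.1 does not fit the restriction in SAP 7.8.

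The size cannot be put as a number of patients. The documents give no rate for such events, and any assumed rate would have no source in them. In scope, the gap concerns one class of event: rehabilitation-related events in the rehabilitation arm (145 planned) and test-related events in both arms (290 planned). Actual numbers may be lower after termination. The primary endpoint and the SAE and AESI tables are not affected.

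The conclusion assumes that the investigator site file and CRF instructions, which are not part of these documents, do not already settle the matter.

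**What to change.** State one rule for which AEs are entered in the CRF, and use it in the flow chart footnote, protocol 5.2.6.2, 8.3.1 and 7.3.4, and SAP 7.8 with 7.8.1. Add to the collected groups a category for non-serious AEs judged related to rehabilitation or exercise testing, with a relatedness field to identify them. Tabulate the category descriptively: rehabilitation-related events in the rehabilitation arm only, since control patients cannot have them, and exercise-test-related events by arm. Bring the overall summary and the other-significant table into line with the rule, or remove them.

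The cost is slightly more data entry, one CRF field and one table. The drawback is higher ascertainment in the rehabilitation arm, where patients have more contact with staff. The report should say so.

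If collection has already closed, the fix reduces to two steps: align the SAP's AE tables to the rule that was actually used and state that rule, and report as a limitation that non-serious harms of rehabilitation were not systematically collected.
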